#### **9.1.3.1.2 Treatment Period (Week 0 through Week 200)**

During the 4-year long-term extension treatment period, subjects will receive 100 mg tildrakizumab, SC, Q12 weeks dosing regimen as described in [Section 9.1](#). The assessments and procedures listed in [Table 9-1](#) will be performed at 12-weekly intervals to Week 104 then 24-weekly intervals to Week 200 and include:

- Record physical examination findings (annually at Weeks 56, 104, 152, and 200 only).
- Perform a urine pregnancy test by urine dip stick (at the site using materials supplied by the central laboratory).
- Perform safety assessments including:
  - perform a 12-lead ECG (annually at Weeks 56, 104, 152, and 200 only),
  - vital signs (all visits except Week 116, 140, 164, and 188),
  - C-SSRS (all visits except Week 140, 164, and 188),
  - routine safety laboratory assessments (hematology, chemistry, and urinalysis, Weeks 20, 56, 104, 152, and 200 only). Blood samples are to be collected (pre-dose) after ECG and vital sign measurements,
  - lipids (Weeks 20, 56, 104, 152, and 200 only),
  - hsCRP and ESR measures at Week 8, 20, 56, 104, 152, and 200 only, to be used for determination of potent AEs should they rise unexpectedly (ESR will be performed at the site using materials supplied by the central laboratory. hsCRP samples will be sent to the central lab and analyzed by central lab),
  - AEs (all visits),
  - record concomitant medications(all visits),
- Obtain a PK sample (Weeks 20, 56, 104, 152, and 200 only).
- Obtain a blood sample for ADA assessments (Weeks 20, 56, 104, 152, and 200 only).
- Administer IMP (Weeks 0, 8, 20, 32, 44, 56, 68, 80, 92, 104, 116, 128, 140, 152, 164, 176, 188, and 200).

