## **8 STUDY OBJECTIVES**

### **8.1 Primary Safety Objectives**

To assess the long-term safety of tildrakizumab when administered to PsA subjects by evaluation of:

- Incidence and intensity of all AEs,
- Changes in vital signs, laboratory assessments, electrocardiograms (ECGs), and Columbia-Suicide Severity Rating Scale (C-SSRS),
- Immunogenicity of multiple-dose administration of tildrakizumab in these subjects.

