- 1 Subjects from the parent Phase 2 study who do not meet inclusion/exclusion criteria at Wk 52 of the parent study (using laboratory data from Wk 48 for efficacy response criteria), or who in the opinion of the Investigator would not benefit from continued treatment with tildrakizumab, will enter the 20-Wk wash-out phase in accordance with the parent protocol (Not shown). All eligible subjects will enter the long-term extension study, commencing at Wk 52 of the parent study (B/L) and receive tildrakizumab 100 mg Q12 wks regimen (Week 0). Subjects who completed the treatment period of their parent study and entered the wash-out phase prior to study site activation of the long-term extension protocol will also be eligible for inclusion in the long-term study (when available) provided they meet eligibility criteria.
- 2 B/L = Wk 0 of the long-term extension study, and will be the same as Wk 52 of the parent study.
- 3 The long-term extension study will remain double-blind for all subjects from the parent Phase 2 PsA study until such point that the PsA study is complete with database locked. At that time, the long-term study will have the option to become open-label for subjects entering from Phase 2 parent study. Note the timing of the switch to open-label may differ across the cohorts of subjects, dependent on the parent study. The IMP administration will continue Q12 weeks, while the safety assessments will be Q12 weeks in the first 2 years, followed by Q24 weeks in the last 2 years.

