**Table 9-1 Schedule of Assessments for PsA Subjects**

Visit a	1	2	3	4	5	6	7	8	9	10	11	12	13	14	15	16	17	18	19	EoT/ FU
Week (± 7D)	0 b	8	20	32	44	56	68	80	92	104	116	128	140	152	164	176	188	200	208 c	
Written informed consent	X																			
Inclusion/Exclusion criteria	X																			
Demographic information d	X																			
Physical examination	X					X				X					X			X	X	
Vital signs	X	X	X	X	X	X	X	X	X		X		X		X	X		X	X	
AEs/Concomitant medications e	X	X	X	X	X	X	X	X	X	X	X	X	X	X	X	X	X	X	X	
Medical/Medication history e	X																			
ECG	X					X				X					X				X	
IMP administration f	X	X	X	X	X	X	X	X	X	X	X	X	X	X	X	X	X	X		
Hematology/chemistry/urinalysis g	X		X			X				X					X			X	X	
Lipids h	X		X			X				X					X			X	X	
Urine pregnancy test i	X	X	X	X	X	X	X	X	X	X		X		X		X		X	X	
hsCRP and ESR i	X		X			X				X				X				X	X	
Anti-drug antibodies	X		X			X				X				X				X	X j	
PK sample h	X		X			X				X				X				X	X	
C-SSRS k	X	X	X	X	X	X	X	X	X	X	X	X	X	X	X	X	X	X	X	

Abbreviations: AE = adverse event; BL = Baseline; C-SSRS = Columbia-Suicide Severity Rating Scale; D = days; ECG = electrocardiogram; ESR = erythrocyte sedimentation rate; EoT = End of Treatment; FU = Follow-up; hsCRP = high sensitivity C-reactive protein; IMP = investigational medicinal product; M = months; PK = pharmacokinetic; PsA = psoriatic arthritis; W = weeks; Y = year(s).

- a Visits will be scheduled every 12 weeks in the first two years, followed by every 24 weeks in the last two years. Collection of AEs and concomitant medications, as well as any unscheduled safety assessment deemed appropriate in the opinion of the Investigator to ensure subject safety, will be performed at each visit. In addition, following completion and database lock of the parent PsA Phase 2 study, the long-term extension study will have the option to become open-label for these subjects.
- b The BL visit of the study Visit 1 (Week 0, Day 1) will be the same as Visit 16, Week 52 of parent PsA study (or later for subjects who entered the wash-out phase from the parent study due to the timing of study site activation of the long-term extension study).
- c Subjects who withdraw from IMP at any time will complete the EoT/FU assessments approximately 4 weeks after administration of the last dose of IMP.

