### **11.4 Assessment of Suicidal Ideation and Behavior**

Subjects will be assessed for suicidal ideation and behavior at Baseline ([Section 9.1.1](#)) and each subsequent visit using the C-SSRS since Last Visit version. There are 5 questions relating to levels of suicidal ideation which prompt questioning about suicidal behavior or intensity of ideation, depending on response. Subjects acknowledging active thoughts of self-harm but lacking an articulated plan for doing so are classified at the intermediate risk level; those presenting a defined self-harm plan or lacking needed impulse control are judged to be at the high-risk level. Subjects who develop suicidal ideation during the study rated as high-risk according to the above classification must be temporarily discontinued from receiving IMP and referred promptly for psychiatric evaluation. Subjects rated as displaying the intermediate level of suicidal ideation should receive psychological support and be assessed on an individual basis. All individuals assessed as exhibiting suicidal behavior, except preparatory acts, must discontinue IMP permanently. The presence of non-suicidal self-injurious behavior should be assessed on an individual basis.

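### Protocol Section 9.1.3.1.2 drops the C-SSRS at Weeks 140, 164 and 188, three dosing visits at which Section 11.4 and Table 9-1 require it

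*Protocol*

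**What the plan says.** Change in the C-SSRS is part of the primary safety objective. Protocol Section 8.1 lists "Changes in vital signs, laboratory assessments, electrocardiograms (ECGs), and Columbia-Suicide Severity Rating Scale (C-SSRS".

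Four places in the current documents give timing specific to this scale:

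- **Protocol Section 9.1.3.1.2:** "C-SSRS (all visits except Week 140, 164, and 188".
- **Protocol Section 11.4:** at Baseline "and each subsequent visit using the C-SSRS since Last Visit version", with no exception.
- **Protocol Table 9-1:** the C-SSRS row carries a mark in every week column from 0 to 208.
- **SAP Section 3.3, amended schedule:** the C-SSRS row is marked at every week from 0 to 200.

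Weeks 140, 164 and 188 are dosing visits. The same Section 9.1.3.1.2 says "Administer IMP (Weeks 0, 8, 20, 32, 44, 56, 68, 80, 92, 104, 116, 128, 140, 152, 164, 176, 188, and 200", and Table 9-1 numbers these weeks as Visits 13, 15 and 17.

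Section 11.4 attaches actions to the result. Subjects with high-risk ideation "must be temporarily discontinued from receiving IMP and referred promptly for psychiatric evaluation", and suicidal behavior other than preparatory acts ends IMP permanently.

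**The concern.** The conflict concerns when a primary safety measure is taken, and no rule says which provision prevails. A site working from the narrative section would skip three structured suicidality screens per completer while still dosing on those days. A site working from the table would skip none.

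The main stake is subject safety. The C-SSRS is the structured trigger for the hold and stop rules in Section 11.4, and skipping it delays the point at which those rules can act. The lesser stake is uneven data. SAP Section 8.7.6 summarizes the scale at each assessment time, SAP Section 7.2.1 imputes nothing, and so the entries at three weeks would depend on which section a site had read.

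**Working it through.** The plan states no count of its own to reproduce, so the check is of marks and intervals.

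**Inputs.** Scheduled weeks (Table 9-1): 0, 8, 20, 32, 44, 56, 68, 80, 92, 104, 116, 128, 140, 152, 164, 176, 188, 200, 208, which is 19 weeks. Dosing weeks (Section 9.1.3.1.2): the same list without 208, which is 18.

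**1. Could broken table extraction explain the conflict?** The Table 9-1 C-SSRS row has 19 marks for 19 weeks. A full row leaves no room for three skipped visits, however the columns shift. The SAP's amended row has 18 marks for 19 weeks; as printed, the empty cell is Week 208. Even if that row were misaligned, at most one week could be unmarked, not three.

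**2. Assessments per completer.**

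| Source followed | Weeks 0 to 200 | Week 208 | Total |
|---|---|---|---|
| Table 9-1 and Section 11.4 | 18 | 1 | 19 |
| Section 9.1.3.1.2 | 18 − 3 = 15 | 1 | 16 |

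**3. Intervals.** Under the table the longest interval is 12 weeks. Under the text three intervals are longer: 152 − 128 = 24, 176 − 152 = 24 and 200 − 176 = 24.

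**4. Delay in detection.** Take ideation that arises between Weeks 128 and 140. The table schedules the next C-SSRS at Week 140 and the text at Week 152, a delay of 152 − 140 = 12 weeks, with the Week 140 dose given meanwhile. The same holds for 164 against 176 and for 188 against 200. Ideation that arises in the second half of a gap is not delayed, so the effect is up to 12 weeks.

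**5. Share of dosing visits affected.** Post-baseline doses: (200 − 8)/12 + 1 = 17, and 3/17 = 17.6%. Doses after Week 104 fall at 116, 128, 140, 152, 164, 176, 188 and 200, which is 8, and 3/8 = 37.5%.

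**6. Does the move to 24-weekly assessment reconcile the texts?** The note to Figure 9-1 in Section 9.1.1 says "the safety assessments will be Q12 weeks in the first 2 years, followed by Q24 weeks in the last 2 years". A schedule built that way after Week 104 would skip 116, 140, 164 and 188. The vital-signs line in Section 9.1.3.1.2 does so: "vital signs (all visits except Week 116, 140, 164, and 188". The Table 9-1 urine pregnancy row leaves the same four weeks blank. The C-SSRS exception keeps Week 116, so it matches neither the 24-weekly pattern nor the table. The SAP's schedule from the original protocol did skip those four weeks, so the exception may be a partly updated leftover; that is inference.

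**The case against.** **The schedule is already named.** Section 9.1.3 identifies Table 9-1 as the schedule and sends the reader to Section 11 for procedures, and Section 9.1.3.1.2 itself opens by invoking Table 9-1. One parenthesis stands against three agreeing sources, and nothing shows how many sites would follow it. This is fair: it makes the intended schedule fairly clear and the split between sites hypothetical. It does not remove an explicit instruction that a site could follow in good faith.

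**A 24-week interval is not itself a defect.** The protocol openly plans less frequent assessment in the last two years. That stands, and the point here is the contradiction, not a preference for 12 weeks. A reader might also infer a third supportable count of 15 by applying the general 24-weekly wording. No C-SSRS-specific line gives 15, so the documents support only 19 and 16.

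**The C-SSRS is not a gate before each dose.** A reader might infer that Section 11.4 and Table 9-1 require it before IMP at every dosing visit. They do not. Only the Baseline procedures in Section 9.1.3.1.1 put it before dosing.

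**Safeguards exist.** AEs are collected at every visit. Table 9-1, footnote a, allows "any unscheduled safety assessment deemed appropriate in the opinion of the Investigator to ensure subject safety". SAP Section 8.7.1 treats ideation and behavior events as events of clinical interest. The form asks about the time since the last visit, so a later form could recover an event for the worst-case table if it covers the whole gap. These reduce the risk. However, the first three rely on reporting or judgment rather than structured questions. As for the form, Weeks 140, 164 and 188 are numbered visits, so read literally the next one looks back only 12 weeks, and nothing tells the rater to go further.

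**Section 9.3.5 is not a second contradiction.** It says IMP may be suspended for suicidal ideation, while Section 11.4 makes the hold mandatory for high-risk ideation. A general permission is compatible with a specific duty. Its pointer to Section 12.4 is a stale number for 11.4, a clerical matter.

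**Conclusion.** The inconsistency is real and should be corrected. Section 9.1.3.1.2 gives an operational instruction that conflicts with Section 11.4, Table 9-1 and the SAP's amended schedule. Its size is three assessments per completer, three intervals doubled from 12 to 24 weeks, and a possible delay of up to 12 weeks in acting on suicidality, with one dose in between.

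The analytic effect is limited. The C-SSRS output is descriptive, and SAP Section 8.7 specifies no statistical tests. Only the by-visit summaries at Weeks 140, 164 and 188 would be incomplete, and the worst-case shift would rest on fewer assessments for the subjects concerned.

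These figures assume a subject who completes to Week 208 at a site that follows the text. The documents give neither the frequency of ideation nor the number of such sites, so no count of missed or delayed events can be given.

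**What to change.** Delete the Week 140, 164 and 188 exception from the C-SSRS line in Section 9.1.3.1.2, so that it agrees with Table 9-1 and Section 11.4. It would be sensible to add that the scale is completed before IMP at dosing visits, but that is a recommendation and not a requirement already in the plan.

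The cost is one deletion and a short questionnaire at three visits that subjects already attend for dosing. No statistical method changes. The references to Section 12.4 in Section 9.3.5 can be corrected to 11.4 as housekeeping in the same amendment.

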#### **9.1.3.1.3 End of Treatment/Follow-Up (Week 208 or Approximately 4 Weeks after Last Investigational Medicinal Product Administration)**

Subjects who complete the study and receive the last scheduled IMP administration at Week 200 will return for a final Follow-up assessment at Week 208 (4 years). In addition,

subjects who withdraw from IMP at any time during this long-term extension study will return for the EoT/Follow-up assessment approximately 4 weeks after administration of their last dose of IMP.

The assessments and procedures listed in [Table 9-1](#) will be performed and include:

- Record physical examination findings.
- Perform a urine pregnancy test by urine dip stick (at the site using materials supplied by the central laboratory).
- Perform safety assessments including:
  - 12-lead ECG,
  - vital signs,
  - C-SSRS,
  - routine safety laboratory assessments (hematology, chemistry, and urinalysis),
  - lipids,
- hsCRP and ESR measures, to be used for determination of potential AEs should they rise unexpectedly (ESR will be performed at the site using materials supplied by the central laboratory. CRP samples will be sent to the central lab and analyzed by central lab),
  - AEs,
  - record concomitant medications.
- Obtain a PK sample.
- Obtain a blood sample for ADA assessments. A final ADA sample needs to be collected after 20 weeks from last dose.

## 9.2 Discussion of Study Design

Subjects with PsA will be eligible for this long-term extension study if they have completed approximately 1 year of treatment in the parent study. At the time of the first subjects entering the long-term extension study, other subjects may still be continuing in the parent Phase 2 study.

The study has been developed based on design features used in the ongoing parent Phase 2 study for PsA subjects as well as ongoing Phase 3 studies for subjects with psoriasis. No efficacy endpoints will be assessed for the study.

The study has been designed to provide an immediate entry into the long-term phase from the end of the parent study with the last assessment from the parent study becoming the Baseline

assessment of the long-term extension. This enables scientific evaluation of safety at all measured time points beyond completion of treatment in the parent study and comparison back to the original Baseline of the parent study. Subjects who entered the wash-out phase of their parent study prior to study site activation of this long-term extension protocol will also be eligible for inclusion and will re-initiate the tildrakizumab dose last received in the parent study. The duration of time in the wash-out phase of the parent study prior to entry to the long-term extension is anticipated to be short, thus enabling continued efficacy assessment across the long-term extension study.

All safety measures are consistent with evaluations used in clinical studies and previous studies with tildrakizumab.

#### **9.2.1 Risk/Benefit and Ethical Assessment**

This extension study will provide subjects from parent Phase 2 study who receive clinical benefit from treatment after approximately 1 year, as determined by eligibility criteria and Investigator opinion, opportunity to receive continued long-term tildrakizumab treatment for up to a further 4 years. Subjects from other studies may also be eligible for entry to this long-term extension study, hence offering extended use of effective dosing regimens.

Subjects will only be eligible for continuation into this long-term extension study if they complete the treatment period of the parent study (Week 48 for parent Phase 2 studies, with return for the EoT assessment at Week 52), meet defined clinical response criteria and, in the opinion of the Investigator, would gain clinical benefit from long-term continuation of tildrakizumab.

The study has also been designed to minimize potential risks to subjects; all subjects will undergo Screening procedures at the start of their parent study aimed at reducing the likelihood and impact of any such risks. In addition, regular safety monitoring during the treatment period of the parent study and this long-term extension study for all subjects will ensure that any unanticipated effects of study participation are identified promptly and managed appropriately. The design also allows withdrawal of subjects from tildrakizumab at the end of the parent study (in accordance with the current parent protocol wash-out phase) and at any time thereafter during the extension study if, in the opinion of the Investigator, the subject is no longer obtaining sufficient clinical benefit, thus enabling subjects to receive other treatment in accordance with local clinical practice.

Overall, based on data from non-clinical and clinical studies of tildrakizumab to date and the risk minimization strategies discussed above, the risk:benefit profile of the current study is considered acceptable.

### **9.2.2 Early Termination**

This study may be terminated at any time by the Sponsor if serious side effects should occur, if the Investigator does not adhere to the protocol or if, in the Sponsor's judgment, there are no further benefits to be achieved from the study. In this event, the Sponsor will inform the study Investigators, institutions and all regulatory authorities.

### **9.3 Selection of Study Population**

#### **9.3.1 Inclusion Criteria**

Subjects may be included in the study if they meet all of the following criteria:

1. Subject has provided written informed consent for this long-term extension study.
2. Subjects with PsA who met the inclusion criteria of the parent study and completed the parent study treatment period (e.g., up to Week 48 for the parent Phase 2 study, with return for the EoT assessment at Week 52).
3. PsA subjects who achieved a 20% reduction from Baseline in American College of Rheumatology (ACR)20 response criteria at Week 52 (for details see [Appendix 22.2](#)), AND the subject has received sufficient clinical benefit, in the opinion of the Investigator, to support continued treatment with tildrakizumab.

Note: This criterion using response criteria at Week 52 of the parent study will apply to all subjects, including those subjects who enter the study from the wash-out phase of their parent study (after Week 52) due to the timing of study site activation of the long-term extension study.

4. No concomitant use of both leflunomide and methotrexate,
5. No history of active tuberculosis (TB) or symptoms of TB.

#### **9.3.2 Exclusion Criteria**

Subjects should be excluded from the study if they meet any of the following criteria:

1. New onset during the parent study of arthritic conditions other than the subject's original condition.
2. Female subjects of childbearing potential who do not agree to abstain from heterosexual activity or practice a dual method of contraception, for example, a combination of the following: (1) oral contraceptive, depo-progesterone, or intrauterine device; and (2) a barrier method (condom or diaphragm). Male subjects with female partners of childbearing potential who are not using birth control as described above must use a barrier method of contraception (e.g., condom) if not surgically sterile (i.e., vasectomy). Contraceptive methods must be practiced upon entering the study and through 16 weeks after the last dose

of IMP. If a subject discontinues prematurely, the contraceptive method must be practiced for 16 weeks following final administration of IMP.

3. Female is pregnant or breastfeeding, or planning to become pregnant or initiate breastfeeding while enrolled in the study or up to 16 weeks after the last dose of IMP.
4. Subject has previously been enrolled in this long-term extension study.
5. Any condition that in the opinion of the Investigator represents an obstacle for study conduct and/or represents a potential unacceptable risk for the subject.
6. Subject has an active infection or history of infections as follows:
  - a serious infection, defined as requiring hospitalization or intravenous anti-infectives within 8 weeks prior to the first IMP dose of the extension study, with the last dose having been received within 7 days of start of the extension study,
  - recurrent or chronic infections, e.g., chronic pyelonephritis, chronic osteomyelitis, bronchiectasis, or other active infection that, in the opinion of the Investigator, might cause this extension study to be detrimental to the subject.
7. Major chronic inflammatory or connective tissue disease other than PsA (e.g., rheumatoid arthritis, systemic lupus erythematosus, Lyme disease, or gout, Crohn's disease, etc).
8. Known diagnosis of fibromyalgia, regional pain syndromes or active uveitis/symptomatic inflammatory bowel disease requiring therapy.
9. Subject has any concurrent medical condition or uncontrolled, clinically significant systemic disease (e.g., renal failure, heart failure, hypertension, liver disease, diabetes, or anemia) that, in the opinion of the Investigator, could cause continued treatment to be detrimental to the subject.
10. Subject has a known history of infection with hepatitis B, hepatitis C, or human immunodeficiency virus during the parent study.
11. Subject had myocardial infarction, unstable angina pectoris, or ischemic stroke within the past 6 months prior to the first IMP dose for this extension study.
12. Subject has any active malignancy, including evidence of cutaneous basal or squamous cell carcinoma or melanoma.
13. Subject has a history of malignancy EXCEPT treated and considered cured cutaneous basal or squamous cell carcinoma, *in situ* cervical carcinoma, OR *in situ* breast ductal carcinoma.
14. Subjects with a history of alcohol or drug abuse during the parent study.
15. Significant risk of suicidality at the Baseline assessment ([Section 9.1.1](#)) of this extension study based on the Investigator's judgment or, if appropriate, as indicated by a response of

"yes" since the last visit to question 4 or 5 in the suicidal section, or any response in the behavioral section of the C-SSRS.

16. Subject has a need for use of a live vaccine within 10 weeks of final anticipated dose of IMP for the long-term extension study.
17. Concomitant use of prohibited medications or use of commercially available or investigational biologic therapies (other than tildrakizumab) for PsO and/or PsA (see [Section 10.6](#)).

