- d To include body weight and height only. Other demographic data including date of birth, sex, and ethnicity will be obtained from the parent study.
- e Report all AEs, SAEs, and concomitant medications that occur after signing of the Informed Consent Form for the long-term study. Any occurring prior to signing the Informed Consent Form for the long-term study should be recorded under Medical/Medication history.
- f IMP administration will occur on Day 1 of Week 0; followed by subsequent dosing Q12 weeks.
- g Blood samples are to be collected (pre-dose where applicable), after ECG and vital sign measurements.
- h At visits where lipids are assessed, the blood samples are to be collected (pre-dose where applicable) after 12 hours fasting, following ECG and vital sign measurements.
- i Urine pregnancy tests will be performed by using a urine dip stick. ESR will be performed at the site using materials supplied by the central laboratory. hsCRP samples will be sent to the central lab and analyzed by central lab.
- j A final anti-drug antibodies sample needs to be collected after 20 weeks from last dose.
- k Evaluations will continue from the parent study using the version with questions referring to 'since the last visit'. No lifetime version will be repeated at BL.

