### 11.3.1 Clinical Laboratory Tests

Unless otherwise indicated, all chemistry and hematology parameters will be analyzed using a central laboratory. The following parameters will be collected:

Laboratory Testing Profile	Tests Included
Blood Chemistry	Sodium, potassium, chloride, bicarbonate/CO 2 , blood urea nitrogen, serum creatinine, fasting glucose, albumin, alkaline phosphatase, AST, ALT, total bilirubin, direct bilirubin, indirect bilirubin, total protein, calcium, gamma-glutamyl transferase, creatine kinase
Hematology	Hemoglobin, hematocrit, WBC with differentials (monocytes, eosinophils, basophils, neutrophils, lymphocytes) as an absolute value, RBC count, platelet count, ESR a
Urinalysis	Specific gravity, pH, semi-quantitative “dipstick” evaluation of glucose, protein, bilirubin, ketones, leukocytes, blood  Microscopy and/or culture to be performed if clinically indicated or if urinalysis results positive (blood, protein or leukocyte esterase/WBC).  Urine hCG pregnancy testing for women of childbearing potential a ; may be repeated more frequently than indicated if required by local practice, if a menstrual cycle is missed, or if potential pregnancy is suspected.

Lipid Panel	Total cholesterol, low density lipoprotein, high density lipoprotein, triglycerides, apolipoprotein A-1, B
Acute-phase Reactants	hsCRP

Abbreviations: ALT = alanine aminotransferase; AST = aspartate aminotransferase; CO2 = carbon dioxide; ESR = erythrocyte sedimentation rate; hCG = human chorionic gonadotropin; hsCRP = high sensitivity C-reactive protein; RBC = red blood cells; WBC = white blood cells.

a Urine pregnancy tests and ESR will be performed at the study site using materials supplied by the central laboratory.

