### **11.3.2 Pregnancy Testing**

For female subjects of childbearing potential, a serum pregnancy test will be performed at the Screening visit of the parent study only. Urine pregnancy test with sensitivity of at least 25 mIU/mL, will be performed according to the Schedule of Assessments ([Table 9-1](#)). If at any point during the study there is a case of a positive urine human chorionic gonadotropin test, the subject will have IMP stopped and will be withdrawn from the study.

Pregnancy tests will also be performed whenever 1 menstrual cycle is missed during the treatment period (or when potential pregnancy is otherwise suspected), to confirm the subject has not become pregnant during the study. Pregnancy tests may also be repeated as per request of IECs/ IRBs or if required by local regulations.

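### For women of childbearing potential, no scheduled pregnancy test or question covers the last part of the 16-week post-dose contraception period; the ADA contact already required after 20 weeks could carry one

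*Protocol*

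**What the plan says.** **Contraception period.** Protocol 9.3.2, criterion 2, applies to everyone entering: "Contraceptive methods must be practiced upon entering the study and through 16 weeks after the last dose". It repeats the rule for early stoppers: "If a subject discontinues prematurely, the contraceptive method must be practiced for 16 weeks following final administration of IMP". Criterion 3 uses the same 16 weeks for planned pregnancy and breastfeeding.

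**Last scheduled test.** Table 9-1 and section 9.1.3.1.3 place the final urine pregnancy test at EoT/Follow-up. Subjects who finish the study and "receive the last scheduled IMP administration at Week 200 will return for a final Follow-up assessment at Week 208". For the others, Table 9-1 note c says: "Subjects who withdraw from IMP at any time will complete the EoT/FU assessments approximately 4 weeks after administration of the last dose of IMP".

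**Event-driven rules.**
- Section 11.3.1 is permissive. The urine test "may be repeated more frequently than indicated if required by local practice, if a menstrual cycle is missed, or if potential pregnancy is suspected".
- Section 11.3.2 is mandatory, but its missed-cycle trigger is tied to the treatment period: "Pregnancy tests will also be performed whenever 1 menstrual cycle is missed during the treatment period (or when potential pregnancy is otherwise suspected".
- Section 11.1.1.12 requires a pregnancy to be reported within 24 hours of awareness and every outcome to be followed. It states no time limit, and it handles miscarriages and birth defects as SAEs.
- Section 11.1.2 collects all SAEs until 30 days after EoT/Follow-up. After that it records only those that are fatal, judged drug-related, or AESIs.
- Section 11.1.1.8 requires prompt notification of an SAE reasonably related to the product at any time after the first dose.

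**A later contact.** Table 9-1 note j adds: "A final anti-drug antibodies sample needs to be collected after 20 weeks from last dose". Section 9.1.3.1.3 and the amended schedule in SAP Table 1 repeat this. The contact has no column in the schedule, and no pregnancy item is attached to it.

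**The concern.** The protocol treats the 16 weeks after the last dose as a period in which conception should be avoided, and it asks for the outcome of all pregnancies to be followed. Yet the last point at which anyone is scheduled to test or ask falls well inside that period. A pregnancy conceived afterwards is recorded only if the subject volunteers it or the site comes to suspect it. The 24-hour rule governs how fast a known pregnancy is reported; it does not make the site aware of one.

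What is at stake is the completeness of follow-up of exposed pregnancies. A blood draw is already required after the contraception period closes, and the plan does not use it to ask the question.

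**Working it through.** The plan states no figure for this gap, so there is none to reproduce. The check is interval arithmetic.

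**Inputs**
- Contraception period: 16 weeks after the last dose (9.3.2).
- Completers: last dose Week 200, EoT/Follow-up Week 208 (9.1.3.1.3), each ±7 days (Table 9-1).
- Early withdrawals: EoT/Follow-up about 4 weeks after the last dose (Table 9-1, note c).
- Dosing interval: 12 weeks (9.1.3.1.2).
- Unrestricted SAE reporting: to 30 days after EoT/Follow-up (11.1.2), and 30/7 = 4.3 weeks.
- Final ADA sample: after 20 weeks from the last dose.

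**Formulas**, with *d* = weeks from the last dose to EoT/Follow-up
- Uncovered weeks = 16 − *d*.
- End of unrestricted SAE reporting, in weeks after the last dose = *d* + 4.3.
- Earliest ADA contact, in weeks after EoT/Follow-up = 20 − *d*.

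| Case | *d* | Uncovered | Share of 16 weeks | Unrestricted SAE reporting ends | ADA contact after EoT/Follow-up |
|---|---|---|---|---|---|
| Completer, nominal | 208 − 200 = 8 | 16 − 8 = 8 | 50% | 8 + 4.3 = 12.3 (3.7 short of 16) | 20 − 8 = 12 (Week 220) |
| Withdrawal, EoT/Follow-up at the nominal 4 weeks | 4 | 16 − 4 = 12 | 75% | 4 + 4.3 = 8.3 (7.7 short) | 20 − 4 = 16 |
| Withdrawal decided and tested at the next 12-weekly dosing visit | 12 | 16 − 12 = 4 | 25% | 12 + 4.3 = 16.3 (past 16) | 20 − 12 = 8 |

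**Visit windows, completers.** Moving both visits by 7 days in opposite directions gives *d* = 8 − 2 = 6 or 8 + 2 = 10, so the gap is 10 or 6 weeks.

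**Withdrawals.** Twelve weeks is the nominal upper figure. It needs the decision to stop to be known by about 4 weeks after the last dose. Because dosing is every 12 weeks, a subject stopped at her next dosing visit is already about 12 weeks post-dose. If she is tested then, about 4 weeks remain. Table 9-1 schedules a urine test at most dosing visits, and EoT/Follow-up includes one.

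**After the fix.** Uncovered weeks = max(0, 16 − 20) = 0 for subjects who attend or are telephoned. The contact falls at least 20 − 16 = 4 weeks after the period closes, so it looks back over all of it. A conception near Week 16 would be only about 4 weeks old at the earliest contact and might not yet be known.

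**The case against.** The strongest reply is that event-driven reporting without a time limit is a coherent design. Section 11.1.1.12 has no cutoff, testing on suspicion is mandatory under 11.3.2, and related SAEs must be notified whenever they are learned of (11.1.1.8, 11.1.2). Active enquiry is an improvement the sponsor may choose; the protocol does not oblige it. That stands, and it is why the point is minor.

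Three stronger readings are tempting, and the documents do not support them.
- *Pregnancy reporting closes 30 days after EoT/Follow-up.* It does not. That limit governs general SAE collection, with exceptions for fatal, drug-related and AESI events. Pregnancy has its own rule.
- *All early withdrawals have 12 uncovered weeks.* They do not. The figure depends on when treatment is stopped and falls to about 4 weeks for a stop at the next dosing visit.
- *The safety results are biased.* Pregnancy is not in itself an AE unless the product is suspected of interfering with contraception (11.1.1.12), and it is not a listed safety endpoint (protocol 12.2.3; SAP 4.2).

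The fix is also not quite free. The ADA contact falls after the Week 208 end of study (protocol 9.1.1) and outside the 208-week maximum duration in SAP 3.3. Putting it in the schedule therefore needs an amendment. That stands and is counted in the cost.

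What the reply does not remove is that every later safeguard depends on someone reporting or suspecting a pregnancy.

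**Conclusion.** The gap is real but minor: a cheap improvement to consider. For women of childbearing potential, no scheduled test or question covers the last 8 weeks of the 16-week period for completers (6 to 10 with visit windows), or about 4 to 12 weeks for early withdrawals (12 if EoT/Follow-up takes place at the nominal 4 weeks). No rule is contradicted, and no planned analysis changes. The gain is more complete follow-up of exposed pregnancies.

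The lower withdrawal figure assumes that a pregnancy test is done at the visit where treatment is stopped. A subject who withdraws consent completely may have no EoT/Follow-up visit, and her gap could be longer. The practical size cannot be stated, because the documents do not give the number of women of childbearing potential. The consent pages were not available, so any instruction there to report later pregnancies could not be checked. The figures do not apply to partners of male subjects: no schedule row asks about partner pregnancy at any time, although 11.1.1.12 requires partner outcomes to be collected.

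**What to change.** 1. At the final ADA contact after 20 weeks from the last dose, ask each woman of childbearing potential about current pregnancy and any pregnancy since the last dose. Ask by telephone if the draw is missed. A question is needed because a test alone would miss a pregnancy that had already ended.
2. Show that contact in Table 9-1 (and the matching SAP schedule) as post-study safety follow-up, with a note reconciling it with the Week 208 end-of-study definition.
3. Do not add a 16-week limit to 11.1.1.12, which now has no cutoff; a limit could narrow it. If wording is wanted, use: *including, but not limited to, pregnancies conceived within 16 weeks of the last dose*.
4. Optionally, ask male subjects at the same contact about known partner pregnancies.

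**Cost.** One CRF item, and an amendment to the schedule and end-of-study text.

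**Limits.** Conceptions near Week 16 may not be known at Week 20. Subjects who fully withdrew consent are generally not reachable, because 9.3.4 bars further contact unless safety findings require it.
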